3.4 Research questions

On these premises, our research questions are:

- is it better to use higher RF powers for shorter times, than lower RF powers for longer times, to reduce the risk of oesophagus overheating and oesophageal temperature alerts?
- is the suggested LSI value of 5 on the LA posterior wall feasible or thwarted by frequent occurrence of temperature alerts leading to premature termination of RF delivery, regardless of maximum power?
- what is the impact of the different RF energy settings on PVI, acute pulmonary vein reconnection (PVR) and short-term clinical success of the AF procedure?
- which LSI value and RF power should be used during RF ablation on the LA posterior wall in order to achieve the best compromise between safety from oesophageal damage and lesion transmuralty and durability?

To these aims, the PiLOT-AF study aims to test different combinations of RF power and LSI during PV encirclement on LA posterior wall.

The rate of oesophageal alerts will be collected and compared for each procedure modality. The rate of first pass PVI and acute PVR (related to breakthrough signals on LA posterior wall), the procedure duration and RF ablation time will be also collected as clinical indicators of lesion transmuralty and acute procedure success. The freedom from AF at 6 months follow-up will be used as clinical indicators of lesion durability and short-term procedure success. The occurrence of any oesophageal symptoms at follow-up will be recorded as surrogate clinical indicators of oesophageal damage. All other procedural complications will be also recorded as safety outcomes.

No data are currently available on this topic. Therefore, this study has been designed as pilot study for power analysis and sample size calculation of a further main study.

This pilot study will hopefully give us some insights about the best combination of RF power, application time and target LSI to use during AF ablation on the LA posterior wall in order to achieve durable PVI with minimal risks of oesophageal damage.

4. OBJECTIVES AND OUTCOME MEASURES

Objectives	Outcome Measures	Timepoint(s) of evaluation of this outcome measure (if applicable)

Primary Objective
 
To compare the risk of oesophageal damage associated with different RF settings during AF ablation on the LA posterior wall
	
Rate of oesophageal temperature alerts (defined as oesophageal temperature rise > 39°C) during RF ablation on the LA posterior wall
	
Index procedure

Secondary Objectives
 
1. To compare the acute success of the index AF ablation using different RF settings on the LA posterior wall
 
2. To compare the short-term success of the index AF ablation using different RF settings on the LA posterior wall
 
3. To compare the rate of oesophageal injury related to different RF settings on the LA posterior wall during the index AF ablation
	
1. Rate of first-pass PVI, rate of acute PVR related to breakthrough signals on the LA posterior wall, total procedure time and RF ablation time
 
2. Freedom from atrial fibrillation
 
3. Rate of oesophageal symptoms (difficult or painful swallowing, heartburn, acid reflux, sore throat, hoarseness, cough, nausea, vomiting, non-cardiac chest pain)
	
1. Index procedure
 
2. During the follow-up period (6 months)
 
3. During the follow-up period (6 months)

Tertiary objectives
 
To evaluate the rate of complications associated with the different RF settings
	
Pericardial effusion, TIA/stroke, phrenic nerve injury, pulmonary vein stenosis, open-heart surgery, death
	
Index procedure

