1. SYNOPSIS

Study Title	Radiofrequency Power, Lesion Size Index and Oesophageal Temperature alerts during Atrial Fibrillation ablation: a pilot study	
Internal ref. no. / short title	PiLOT-AF study	
Study Design	Prospective, randomized, single centre observational clinical investigation	
Study Participants	Patients admitted for elective radiofrequency (RF) ablation for paroxysmal or persistent atrial fibrillation (AF)	
Planned Sample Size	80 patients (pilot study)	
Planned Follow-up duration	6 months	
Planned Study Period	15 months	
	Objectives	Outcome Measures
Primary	Assessment of the risk of oesophageal damage associated with radiofrequency (RF) ablation on the left atrial (LA) posterior wall when using different power settings	Luminal oesophageal temperature rises > 39°C during RF application on the LA posterior wall as recorded by an oesophageal temperature probe
Secondary	
Comparison of oesophageal complications with the different RF settings on LA posterior wall
 
Comparison of acute and short-term procedure success using different RF settings on LA posterior wall as marker of lesion transmural and durability
	
Symptoms of oesophageal injury during 6 months follow-up
 
Rate of first-pass pulmonary vein isolation (PVI), rate of acute pulmonary vein reconnection (PVR), total procedure time and RF time of the index ablation procedure
 
AF-free survival during 6 months follow-up

Tertiary	Comparison of rate of procedural complications using the different RF settings	pericardial effusion, TIA/stroke, phrenic nerve injury, pulmonary vein stenosis, open-heart surgery, death

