Lower RF powers and shorter application times are usually used on the LA posterior wall but this is a completely empirical approach which has not been proved to be effective in preventing oesophageal damage. Continuous luminal oesophageal temperature monitoring during the AF procedure is a suggested strategy to prevent oesophageal damage related to AF ablation. The rationale behind this strategy is that luminal oesophageal temperature is a surrogate marker of the mural temperature and therefore it can predict and avoid tissue damage. Observational studies employing real-time luminal oesophageal temperature measurements during LA catheter ablation have shown that lower oesophageal luminal temperatures are associated with lower rates of oesophageal ulcerations detected by endoscopy after ablation (30-33). To this aim, a temperature probe is inserted nasally or orally and advanced to the level of the posterior LA under fluoroscopic guidance where it permits real-time intraluminal oesophageal temperature monitoring during the ablation. Moreover, it marks the location of the oesophageal lumen that can also be visualized in the electro-anatomical map to evaluate the distance of the ablation catheter tip from it. Different oesophageal temperature probes are currently available: single-sensor ones, linear multi-sensor and 2-dimensional sinusoidal multi-sensor ones. The advantage of the multi-sensor probes, and especially of the sinusoidal one, is that their design allows for a greater area of temperature monitoring and their position does not require adjustments to be in close vicinity of the ablation catheter tip during RF delivery (34).

When using an oesophageal temperature probe-guided ablation strategy, RF delivery on the LA posterior wall is promptly terminated in case of any oesophageal temperature rises $>39^{\circ}\text{C}$ and power is reduced in contiguous sites. However, the big challenge of this approach is in not knowing how much delivered RF energy is both simultaneously “safe” and “effective”.

In our experience, oesophageal temperature alerts are very common during PV encirclement on LA posterior wall, occurring in the majority of procedures and, regardless of the power used, they tend to occur before the achievement of the suggested LSI of 5. Moreover, lower RF powers are generally used on LA posterior wall but, in view of the strict relation between power and application time in determination of

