- *LA ablation strategy and technique.* The PVs will be encircled in pairs to isolation using an irrigated-tip ablation catheter TactiCath Quartz (SJ Medical, St Paul, MN, USA) via an Agilis deflectable sheath. A point-by-point ablation technique will be used, with a minimum CF of 10 g and a target CF of 20 g for each RF lesion. As current practice, the circumferential ablation line around the PV pairs will be predefined on the electroanatomical LA map, at 1-2 cm from PV ostia with individual adjustments in order to avoid RF delivery in close proximity of the oesophageal probe.

- *RF settings on the LA anterior wall, roof and floor.* As current practice in our centre, an RF power of 40 W will be used on LA anterior wall, roof and floor. The RF application time will be dictated by the achievement of the target FTI and LSI (FTI \geq 400 gs; LSI \geq 6 on LA anterior wall and LSI \geq 5.5 on LA roof and floor).

- *RF settings on the LA posterior wall.* Different RF settings will be used during RF ablation on LA posterior wall, according to randomization group:

- ✓ *Group 1:* 20 W RF power, with target LSI = 4;
- ✓ *Group 2:* 40 W RF power, with target LSI = 4;
- ✓ *Group 3:* 20 W RF power, with and target LSI = 5;
- ✓ *Group 4:* 40 W RF power, with target LSI = 5.

Regardless of the LSI achieved, RF delivery on the LA posterior wall will be promptly terminated in case of any oesophageal temperature rise \geq 39°C or after 60 seconds of continuous RF delivery. The ablation catheter will be then moved to a contiguous lower or higher site on the predefined circumferential ablation line.

- *PVI confirmation.* Disappearance of PV potentials or dissociated PV potentials in the vein and inability to capture the LA during PV pacing will confirm bidirectional block across the PV circumferential ablation line and PVI.

- *Waiting time.* After a waiting time of 30 min, the PVs will be rechecked in order to confirm the persistence of PVI.

- *Acute PVR.* In case of acute PVR, additional RF ablation will be performed in correspondence of breakthrough signals. The same RF settings of the first PV encirclement will be used.

- *Procedure completion.* The procedure will be terminated after achievement of electrical isolation of all PVs. A trans-thoracic echocardiogram will be performed at the end of the procedure to rule out the presence of pericardial effusion. Protamine will be administered to reverse heparin.

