11. STATISTICS AND ANALYSIS

11.1. The Number of Participants

The PiLOT-AF study aims to give some insights about the relation among RF power, LSI and incidence of oesophageal temperature alerts during AF ablation on the LA posterior wall. In view of the absence of data on this topic, it has been designed as pilot study for power analysis and sample size calculation of a further main study.

As suggested before for pilot studies (38), we aim to a final sample size of 12 patients with primary outcome data per each treatment group. We know from previous studies that oesophageal temperature alerts occur in 55-75% of AF ablations. Therefore, if taking into account also participants who do not experience oesophageal temperature alerts during AF ablation, we plan to recruit a total of 80 patients in order to achieve primary outcome data in 12 patients per group.

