11.2. Description of Statistical Methods

Comparison of primary, secondary and tertiary outcome measures among different treatment groups will be performed at each time point using appropriate statistical testing. In particular, ANOVA tests will be used to compare numerical variables and chi-square tests will be used to compare categorical values.

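### The primary outcome, a rate of oesophageal temperature alerts, has no unit of analysis, and the plan does not rule out pooling correlated applications or discarding the number of alerts

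*Combined protocol and SAP*

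**What the plan says.** The primary outcome appears in three places in the combined protocol and SAP. Section 4 gives "Rate of oesophageal temperature alerts (defined as oesophageal temperature rise > 39°C) during RF ablation on the LA posterior wall". The synopsis (section 1) gives "Luminal oesophageal temperature rises > 39°C during RF application on the LA posterior wall as recorded by an oesophageal temperature probe". Section 3.4 adds: "The rate of oesophageal alerts will be collected and compared for each procedure modality". None of them names a denominator.

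Alerts arise at the level of a single lesion. Section 9 states: "A point-by-point ablation technique will be used, with a minimum CF of 10 g and a target CF of 20 g for each RF lesion". Under the same section an alert stops delivery at the site concerned and the catheter moves to a neighbouring one, so a patient can have none, one or several.

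The statistics sections do not settle the unit. Section 11.1 cites a per-procedure figure: "We know from previous studies that oesophageal temperature alerts occur in 55-75% of AF ablations". It then inflates recruitment to 80 so that 12 patients per group have primary outcome data, on the ground that some patients will have no alert. Section 11.2 assigns ANOVA to numerical variables and says "chi-square tests will be used to compare categorical values". It does not say which test applies to the primary outcome, does not mention repeated applications within a patient, and states no significance level.

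**The concern.** At least three outcomes fit the wording: the share of patients with any alert, the share of applications with an alert, and the number of alerts per patient. They have different statistical properties and need different tests.

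Applications in one patient share that patient's anatomy. Section 3.3 stresses that oesophageal position, wall thickness and the intervening tissue vary, so positive within-patient correlation is to be expected. A test that treats applications as independent would then understate the standard error. A yes/no score per patient avoids that problem but counts one alert and ten alerts alike.

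The rule on who supplies primary outcome data adds to the difficulty. Under a yes/no outcome an alert-free patient is a valid observation. Under a proportion or a count the same patient is a zero. Treating such patients as without data fits none of these.

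The study exists to size a main trial (sections 3.4 and 11.1), and a rate without a unit cannot be carried into a sample-size formula. The investigator knows the allocation (section 8.2.3), so a unit chosen after the data are seen would be open to challenge.

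**Working it through.** **1. The plan's own figure.** Recruitment per group = 12 / (share of patients with an alert), rounded up, times 4 groups.

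- 55%: 12/0.55 = 21.8, so 22 per group, 88 in total
- 60%: 12/0.60 = 20 per group, 80 in total
- 65%: 12/0.65 = 18.5, so 19 per group, 76 in total
- 75%: 12/0.75 = 16 per group, 64 in total

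The planned 80 is reproduced at 60%, which the plan does not state but which lies inside its range. The division confirms that alert-free patients are treated as missing.

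**2. Pooled applications, ordinary chi-square.** From the documents: 4 arms of 20 patients (section 8.2.3). Assumed: m posterior-wall applications per patient, equal in all patients; ICC; a 5% level.

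Design effect DE = 1 + (m - 1) x ICC. Type I error = P(chi-square on 3 df > 7.815/DE).

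- m = 5, ICC 0.02: DE = 1 + 4 x 0.02 = 1.08; 7.815/1.08 = 7.24; error 6.5%
- m = 30, ICC 0.20: DE = 1 + 29 x 0.20 = 6.8; 7.815/6.8 = 1.15; error 76.5%

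| m | ICC 0.02 | ICC 0.05 | ICC 0.10 | ICC 0.20 |
|---|---|---|---|---|
| 5 | 6.5% | 8.9% | 13.4% | 22.7% |
| 10 | 8.5% | 14.5% | 25.0% | 42.5% |
| 20 | 12.9% | 26.1% | 44.1% | 65.3% |
| 30 | 17.6% | 36.3% | 57.2% | 76.5% |

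A beta-binomial simulation (10,000 null trials per cell, any-alert probability held at 55%, 65% or 75%) agrees to within about 1 percentage point. At ICC 0 there is no inflation (4.4-5.2%).

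**3. Patient as the unit, same simulations.** ANOVA on per-patient alert counts rejects in 4.3-5.3% of null trials, and chi-square on any alert per patient in 4.4-5.5%. Both are valid.

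**4. Is any-alert at a ceiling?** The binomial variance p(1 - p), against its maximum of 0.25, is 0.55 x 0.45 = 0.2475 (99%) at 55% and 0.75 x 0.25 = 0.1875 (75%) at 75%. The chance that all 20 patients in an arm have an alert is at most 0.75^20 = 0.3%. So the outcome is mid-range. It is weak mainly because the sample is small: power for 55% v 75% is 26% with 20 v 20 and 47% with 40 v 40. Upward room is limited only from the top of the range. From 75%, no higher rate reaches 80% power with 20 per arm, whereas a fall to about 32% does.

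**5. Information lost by any-alert.** The per-application probability p is set so that any-alert is 55% or 75%, then doubled in one group. The comparison is 40 v 40 (two arms combined per power level), with m from 5 to 30 and ICC from 0.02 to 0.20. For example, at m = 20 and ICC 0.10, p = 0.072 gives any-alert 55%, and p = 0.144 gives about 80%. From 75%, doubling gives about 95%. Across the grid:

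- chi-square on any alert per patient: power about 67-87%
- rank test on per-patient burden: power about 78% to over 99%

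With m equal in all patients, ranking the count and ranking the proportion are the same test.

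**The case against.** The strongest defence is that the plan already contains a sound analysis. Alerts per patient is a numerical variable, section 11.2 gives numerical variables ANOVA, and that holds about 5%. Section 11.1 counts patients and cites a per-procedure rate, which points to the patient as the unit. This is an 80-patient pilot, and application-level data, if kept, would allow any unit to be derived later. Most of this stands, but permitting a valid analysis is not the same as choosing it, and deriving the unit later is what prespecification is meant to prevent.

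Three stronger readings are tempting, and the documents do not support them.

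- A reader might infer that any-alert starts near its ceiling, because section 3.3 says "oesophageal temperature alerts are very common during PV encirclement on LA posterior wall, occurring in the majority of procedures". That gives no number, and the only figure in the plan, 55-75%, is mid-range. A near-ceiling rate needs outside assumptions, such as a 20% alert risk per application with 20 or more applications (90% or more at ICC 0.10).
- A reader might infer that the trial will have a false-positive rate far above 5%. Nothing in the plan commits to pooling applications. The inflation is conditional on a choice left open, and its size rests on an application number and an ICC that the documents do not give.
- A reader might infer that every available analysis is poor. The ANOVA route shows otherwise.

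A fair objection to the remedy also stands. The number of posterior-wall applications is observed after randomisation and may differ by arm, since an alert moves the catheter to a new site and reconnection adds applications.

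**Conclusion.** The concern holds as an undefined unit, made worse by a sample-size rule that leaves alert-free patients out of the primary outcome data. Both follow from the documents alone.

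The consequences are conditional. Pooling with an ordinary chi-square would raise the type I error from 5% to between about 6.5% and 76.5% over 5-30 applications and ICC 0.02-0.20. Scoring any alert per patient would be valid but would give up power: about 67-87% against about 78% to over 99%. The application numbers, ICC, 5% level, doubling of risk, equal application counts and 40 v 40 contrast are all assumptions. This should be corrected before analysis, but it does not show that the planned trial is invalid.

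**What to change.** In sections 1, 4 and 11, name the patient as the unit. Define the primary outcome as alert burden per patient: posterior-wall applications with an alert divided by all posterior-wall applications. Score alert-free patients as zero, so that every treated patient contributes, and amend section 11.1 to match. Compare arms with a patient-level test (for example, a rank test on the per-patient proportion) or a patient-clustered binomial model. State that applications are never pooled as independent. Report the per-patient alert count and any alert per patient as supportive outcomes.

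The event being counted also needs one definition: sections 1, 4 and 5 put the alert above 39°C, while section 9 includes 39°C itself. These passages must be reconciled.

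The cost is two counts on the CRF and revised wording, with no extra patients or procedures. There are two drawbacks. The headline figure is less directly comparable with published per-procedure rates, which the any-alert figure covers. The denominator arises after randomisation and may differ by arm, which the supportive count and any-alert figures address because neither uses it.

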5. STUDY DESIGN

The PiLOT-AF study is a prospective single-centre randomized observational study aiming at comparing different RF settings during AF ablation on the LA posterior wall, in terms of oesophageal heating, acute and long-term procedure success and procedural complications.

Patients, age 18-80, scheduled for their first RF ablation because of a history of symptomatic and drug-refractory paroxysmal or persistent atrial fibrillation, will be considered for inclusion in the study.

Potential subjects will initially be approached 4-6 weeks before their ablation procedure, in order to give the patients enough time to consider the information, to ask questions to the Investigator, their GP or other independent parties to decide whether they wish to participate in the study or not.

For those interested in participation, a baseline assessment will be arranged to coincide with their standard pre-admission visit, for informed consent, screening and eligibility assessment and randomization.

All AF ablation procedures will be performed in a standard fashion, under general anaesthesia and with continuous oesophageal temperature monitoring using a sinusoidal multi-sensor oesophageal temperature probe (CIRCAtemp). After LA geometry reconstruction using 3-dimensional electroanatomical mapping EnSite Velocity and a multipolar circular mapping catheter St Jude Medical Optima, a CF ablation catheter Endosense TactiCath through a deflectable sheath St Jude Medical Agilis will be used for PVI. Standardized RF settings will be used during ablation on the LA anterior wall as current practice in our centre. Different RF settings will be used on the LA posterior wall, according to randomization group. Duration of RF delivery on the LA posterior wall will be dictated by achievement of target LSI or oesophageal temperature rise $> 39^{\circ}\text{C}$ during ablation. PVI will be achieved and confirmed after 30 minutes waiting time. In case of acute PV reconnection, ablation at sites of breakthrough signals will be performed in order to achieve durable PVI. The occurrence of acute PV reconnection with sites of breakthrough signals on the LA posterior wall will be recorded for each procedure. The total procedure and RF ablation times will be also collected.

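### RF time, and probably first-pass PVI, are compared over the whole ablation circle although only posterior-wall settings are randomised, which costs sensitivity in secondary outcome 1

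*Combined protocol and SAP*

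**What the plan says.** Sections 8.2.3 and 9 assign four combinations of power and target LSI, and these apply on the LA posterior wall only. Elsewhere on the circle the settings are common to all arms: "an RF power of 40 W will be used on LA anterior wall, roof and floor", with common FTI and LSI targets.

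Secondary outcome 1 in section 4 lists four measures: "Rate of first-pass PVI, rate of acute PVR related to breakthrough signals on the LA posterior wall, total procedure time and RF ablation time". The posterior-wall qualifier is attached only to acute reconnection.

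- **RF time.** The synopsis gives its scope as "total procedure time and RF time of the index ablation procedure". Section 5 says "The total procedure and RF ablation times will be also collected", with no split by wall.
- **First-pass PVI.** It has no definition of its own. Section 9 says "The PVs will be encircled in pairs to isolation" and confirms success by "bidirectional block across the PV circumferential ablation line and PVI", which is a whole-circle criterion. Section 3.4, however, writes "The rate of first pass PVI and acute PVR (related to breakthrough signals on LA posterior wall" and closes the bracket there, and that bracket could be taken to cover both measures.
- **Acute PVR.** Sections 3.4, 4 and 5 tie it to posterior breakthrough. The synopsis does not: "rate of acute pulmonary vein reconnection (PVR), total procedure time and RF time of the index ablation procedure".

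**The concern.** Secondary objective 1 asks how the posterior-wall settings affect acute success. RF delivered to the anterior wall, roof and floor follows the same settings in every arm, so its duration says nothing about the randomised contrast, yet it enters total RF time. A residual gap on one of those segments would likewise count as a first-pass failure if the measure is scored on the whole circle. The sponsor has already limited acute PVR to the posterior wall; the companion measures do not follow the same logic.

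Section 3.4 treats these measures as indicators of transmurality and acute success, the effectiveness side of the compromise that the study wants to find. Section 3.3 expects lower power to mean longer applications, so posterior RF time is where a difference should appear. The pilot is also meant to support sample size planning for a main study. If these measures are used for that, the extra variance goes into the planning.

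**Working it through.** **The plan's own figure.** The only sizing in section 11.1 is for the primary outcome: 12 patients with data per group and an alert rate of 55-75%. At 60%, 12 / 0.60 = 20 per arm and 4 x 20 = 80, which matches. Section 8.2.3 agrees: 4 blocks x 5 per arm = 20. No SD, rate or power is given for first-pass PVI or RF time, so every input below other than the arm size and the type of test is an assumption, including the 5% level (two-sided for pairwise comparisons).

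**RF time.** Write total time = posterior time + other-wall time, taken as independent. The other-wall mean is the same in all arms, so the expected difference between arms in minutes is unchanged. The variance becomes SD_post² + SD_other².

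Under the ANOVA of section 11.2 with 20 per arm, let the power setting change posterior RF time by 3 minutes and LSI have no effect. Each arm mean then lies 1.5 minutes from the grand mean. The noncentrality is 20 x 4 x 1.5² / variance = 180 / variance, on 3 and 76 degrees of freedom. Posterior SD is 4 minutes.

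| Measure | Variance | Noncentrality | Power |
|---|---|---|---|
| Posterior RF time | 16 | 11.25 | 79% |
| Total, other-wall SD 4 | 16 + 16 = 32 | 5.63 | 47% |
| Total, other-wall SD 6 | 16 + 36 = 52 | 3.46 | 30% |
| Total, other-wall SD 8 | 16 + 64 = 80 | 2.25 | 20% |

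Varying the assumed effect in the same formula:
- 2 minutes (80 / variance): 42% falls to 22%, 15% and 11%.
- 4 minutes (320 / variance): 97% falls to 74%, 51% and 34%.

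For sizing a later two-group comparison with a true difference of one posterior SD and equal SDs on the two parts, the standardised effect falls from 1.00 to 1/√2 = 0.71. The number per arm for 80% power then rises from 16 to 32.

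**First-pass PVI, if scored on the whole circle.** Let q be the chance that the non-posterior part is isolated at first pass, the same in all arms and independent of the posterior part. The observed rate is q x posterior success, so the difference between arms is multiplied by q. With posterior success of 60% v 90%, compared pairwise at 20 v 20:

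| q | Rates | Difference | Power |
|---|---|---|---|
| 1 (posterior only) | 60% v 90% | 30 points | 60% |
| 0.9 | 54% v 81% | 27 points | 44% |
| 0.8 | 48% v 72% | 24 points | 34% |
| 0.6 | 36% v 54% | 18 points | 20% |

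With 70% v 90%, the difference goes from 20 points to 16 at q = 0.8, and power from 35% to 18%. These are pairwise figures, not the planned four-group chi-square test; they show the direction and the shrinkage.

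**The case against.** Several points on the other side have force.

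- **First-pass scope.** A reader might infer that the plan definitely scores first-pass PVI on the whole circle. It does not say so. The bracket in section 3.4 allows a posterior-only reading. The outcome table and the definition of PVI point the other way, but this is inference. What is established is that the measure needs a definition.
- **Meaning of dilution.** A reader might infer that both measures are pulled towards no difference. That is wrong for RF time, where the expected difference is unchanged and only precision is lost. Only the first-pass difference shrinks, and only under the whole-circle reading.
- **Legitimate target.** Section 4 asks about success of the index procedure, and whole-procedure values are meaningful clinical measures. This stands, and is why they should be kept. It does not make them sensitive to a contrast confined to one wall. Acute PVR already gives one posterior-specific indicator, so not every acute-success measure is affected.
- **Size.** Pooling arms to 40 v 40 would give higher starting power (91% for posterior RF time on the same inputs), but no such contrast is planned. Even the four-arm figures rest on assumed SDs and effects.
- **Judging gap site.** The investigator knows the allocation (section 8.2.3). Attributing a gap to the posterior wall is more open to judgement than the electrical criteria for isolation in section 9. This stands and limits the fix.

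**Conclusion.** The point holds as a loss of sensitivity. It is explicit for RF time, whose whole-procedure scope is in the text. It is conditional for first-pass PVI, whose scope is inferred. Total procedure time has the same feature. No arm is favoured: the other segments have common settings, although the ablation actually delivered there still varies from patient to patient.

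The documents support no single figure for the loss. The four-arm fall from 79% to between 47% and 20% depends on the assumed 3-minute effect, the SDs, no LSI effect and independence of posterior and other-wall time. A positive correlation would add further variance and a negative one would remove some. The direction for RF time needs only that other-wall time varies and is not strongly negatively correlated with posterior time.

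The weight is moderate: these are secondary outcomes of a pilot with no stated power. A reader might infer that the acute-success comparison is invalid or biased, and the documents do not support that. The synopsis wording on acute PVR is an alignment matter only.

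**What to change.** In section 4 and the synopsis:

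1. Make posterior-wall RF time the compared RF-time measure, and report total RF time and total procedure time alongside.
2. Define first-pass PVI: the part of the circle it covers and the unit (patient, PV pair or vein). Keep any-site first-pass PVI as a compared outcome.
3. Record the site of any residual gap at first encirclement, as is already done for acute PVR, and add first-pass failure with a posterior-wall gap as a supporting comparison.
4. Give acute PVR the same posterior-wall definition in the synopsis as in section 4.

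The cost is small but not nil. Operators must already distinguish posterior applications, because the settings and the alert count depend on it. Section 5 mentions only total times, however, so RF duration would have to be summed by segment. One CRF field is needed for gap site. That site would be judged by an operator who knows the arm, which is why it should support the any-site result and not replace it. No change to treatment is involved.
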